### 7.3.4 Severe Vitamin D Deficiency

Age	1-3 years	Vitamin D	Calcium (elemental)
Vitamin D level (D 2 +D 3 ) F	<10		
dietary calcium intake			
PTH			
Ionized or corrected Calcium		
 
• Vitamin D 50000 IU (single dose) ; then 4000 IU/day starting day 2 for 8 weeks
 
• Vitamin D (D2+D3) should be checked in 8 weeks and continue vitamin D if still low
 
• Once Vitamin D normalized the participant would receive 600 IU/day of Vitamin D.
 
	
 
• calcium 50 mg/kg divided 3x/day (max daily calcium dose of 2.000 mg/day) for 4 weeks
 
• Check ionized or corrected calcium every week and if low increase supplementation as needed to normalize ionized or corrected calcium
 
• Once ionized or corrected calcium is normalized, if dietary calcium intake is low, the participant will receive calcium 600 mg/day
 

Age	4-8 years	Vitamin D	Calcium (elemental)
Vitamin D level (D 2 +D 3 ) T	<10	
 
Vitamin D 50000 IU (single dose); then 4000 IU/day starting day 2 for 8 weeks
 
	
 
calcium 50 mg/kg divided 3x/day (max daily calcium dose of 2.000 mg/day) for 4 weeks
 

dietary calcium intake			
PTH			
Ionized or corrected Calcium		
 
Vitamin D (D2+D3) should be checked in 8 weeks and continue vitamin D if still low
 
Once Vitamin D normalized the participant would receive 600 IU/day of Vitamin D.
 
	
 
Check ionized or corrected calcium every week and if low increase supplementation as needed to normalize ionized or corrected calcium
 
Once ionized or corrected calcium is normalized, if dietary calcium intake is low, the participant will receive calcium 1,000 mg/day
 

Age	$\geq 9$	Vitamin D	Calcium (elemental)
Vitamin D level ( $D_2+D_3$ ) T	<10	
 
50000 IU (single dose) on day 1; and then starting day 2, give 50000 IU (single dose) every week for 8 weeks x 9 doses total
 
	
 
calcium 50mg/kg/day divided 3x/day (max daily calcium dose of 2.000 mg/day) for 4 weeks
 

dietary calcium intake			
PTH			
Ionized or corrected Calcium		
 
Vitamin D (<math>D_2+D_3</math>) should be checked in 8 weeks and continue vitamin D if still low
 
Once Vitamin D normalized the participant would receive 600 IU/day of Vitamin D.
 
	
 
Check ionized or corrected calcium every week and if low increase supplementation as needed to normalize ionized or corrected calcium
 
Once ionized or corrected calcium is normalized, if dietary calcium intake is low, the participant will receive calcium 1,200 mg/day
 

Age	<9	Vitamin D	Calcium (elemental)
TPN	No Oral Intake	
 
give 50000 IU (single dose) of vitamin D on day 1; and then starting day 2, 50000 IU (single dose) every other week x 5 doses total
 
Vitamin D (<math>D_2+D_3</math>) should be checked in 8 weeks and continue vitamin D if still low
 
Once normalized the participant would receive 600 IU/day of Vitamin D
 
	
 
calcium supplementation 50 mg/kg/day or the maximum allowed per TPN
 

Age	<math>\geq 9</math>	Vitamin D	Calcium (elemental)
TPN	No Oral Intake	
 
give 50000 IU (single dose) of vitamin D every week x 8 doses total
 
Vitamin D (<math>D_2+D_3</math>) should be checked in 8 weeks and continue vitamin D if still low
 
Once normalized the participant would receive 600 IU/day of Vitamin D
 
	
 
calcium supplementation 50mg/kg/day or the maximum allowed per TPN
 

*If a subject's total calcium level is below the normal range at any time, calculate a corrected calcium if a serum albumin level is available (may have been drawn anytime within 7 days of the calcium level) using the formula:*

$$\text{Corrected Ca mg/dl} = \text{measured total Ca mg/dl} + [0.8 (4.0 - \text{serum albumin g/dL})]$$

*If a serum albumin level is not available ionized calcium level should be done.*

**VITAMIN D PREPARATIONS:**

Over-the-counter (OTC): Cholecalciferol (preferred) or Ergocalciferol 400 IU, 800 IU, 1,000 IU, 2,000 IU, 4,000 IU, or 400 IU/ml

Prescription (Rx): Cholecalciferol (preferred) or Ergocalciferol 50,000 IU gel capsules or tablets prescribed for once weekly administration, Ergocalciferol 8,000 IU/ml

**CALCIUM PREPARATIONS:**

Over-the-counter (OTC): Calcium Carbonate: e.g., TUMS 500 mg (200 mg elemental calcium,), TUMS 750 mg (300 mg elemental calcium), TUMS 1,000 mg (400 mg elemental calcium), or TUMS kids 750 mg (300 mg elemental calcium) cherry flavored.

Rx: Calcium Carbonate: Oral suspension 1,250 mg/5 ml (elemental calcium = 500 mg/5 ml)

**7.4 Pamidronate**

**7.4.1 Treatment Plan**

Subjects randomized to the Pamidronate Group will receive 3 single doses of pamidronate at 3-month intervals (Day 90 +/-14 days, Day 180 +/-14 days, and Day 270 +/-30 days).

Note: All time point specific laboratory testing procedures (sections 8.1 and 8.3) must be collected prior to the pamidronate infusion (except those specifically designated post infusion); however for ease of scheduling the consultations as well as the Day 90 DXA and Day 90 pQCT may be performed after the infusion as long as done within the +/-14 day window. Ionized calcium or corrected calcium, and Vitamin D levels (D2+D3) will be drawn prior to pamidronate infusions. If either are low, the subject should receive supplemental calcium and/or Vitamin D per Section 7.3. If the subject is receiving supplemental calcium, an ionized or corrected calcium level should be drawn after the pamidronate infusion end but prior to discharge from clinic on the day of the pamidronate.

Prior to each infusion the patient will be assessed and pamidronate will be held if:

- Serum creatinine is > 2 times the baseline (Study Entry) level – refer to section 7.3.2 for monitoring plan – the pre-treatment creatinine may be done anytime within 72 hours prior to the planned pamidronate administration

- Pregnancy test is positive (subject will permanently discontinue study drug) per section 7.3.5 – pregnancy testing may be done anytime within 72 hours prior to the planned pamidronate administration

Pamidronate 1 mg/kg (to a max dose of 60 mg) will be administered via a single IV infusion over 4 hours using a line separate from all other drugs. Dosing will be based on the patient's actual weight or, if overweight, on ideal body weight (IBW). This will be followed by a normal saline flush of 20 cc total given at the same rate as the pamidronate.

Premedication: Subjects will be given 15 mg/kg acetaminophen (or maximum of 500 mg) prior to pamidronate infusion then every 4 hours as needed for a maximum of 24 hours.

Post-Pamidronate Infusion Laboratory Tests: A serum calcium level will be done after the pamidronate infusion end but prior to discharge from clinic on the day of the pamidronate.

A serum creatinine and a spot urine albumin and creatinine will be scheduled for the morning after each pamidronate infusion in the outpatient lab; however, some flexibility in timing is permitted and it will not be considered a deviation if testing is done within 7 days post-infusion. A morning collection is preferred, but not mandatory. The time of the urine collection must be recorded. If done at an outside lab, the institutional study coordinator will oversee the necessary arrangements for testing and receipt of the results.

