### **6.2 Randomization (Day 90 Post-HCT Visit +/- 14 days)**

Randomization to pamidronate (Pamidronate Group) or no pamidronate (Control Group) will occur at Day 90 (+/- 14 days) by the institutional study coordinator based on the randomization schedule developed by the study statistician and entered into OnCore.

A brief review of continuing eligibility will be done and subjects will not be eligible for randomization if one or more of the following are true:

- Vitamin D ( $D_2+D_3$ )  $<20$  ng/ml as use of pamidronate is contraindicated due to potentially higher risk of hypocalcemia. Levels should be measured within 14 days prior to randomization.\*\*†
- serum creatinine is  $> 2$  times the baseline value (at Study Entry) - perform within 14 days prior to randomization
- an investigational study drug or agent, including biphosphonates, Denosumab, or Teriparatide, was administered within the previous 4 weeks or is planned for use during study participation (Day 90 through Day 360)
- positive pregnancy test (performed within 14 days prior to randomization)
- Inability to successfully complete a DEXA scan
- the parent or adult patient refuse randomization
- disease relapse has occurred

The randomization will be stratified by age with 2 strata:  $< 10$  years old and  $\geq 10$  years old.

If the patient is ineligible for or refuses randomization, no further research related procedures or treatment will occur after the Day 90 visit; however permission to continue review of the patient's medical record through the Day 360 visit for routine clinical information is embedded within the consent form document. This information will be collected only if the patient continues care at the enrolling

institution. Patient care will be at the discretion of the treating physician(s) and independent of this study.

OnCore will automatically generate an email alerting key study personnel of the randomization (or lack of).

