dietary calcium intake based on questionnaire	Low or normal	
 
Once the Vitamin D level is normalized the participant would receive 600 IU/day of Vitamin D
 
	
 
Once ionized or corrected calcium is normalized, if dietary calcium is low, the participant would receive calcium 1,000 mg/day
 

Age	$\geq 9$	Vitamin D	Calcium (elemental)
Vitamin D level ( $D_2+D_3$ ) T	20-29	
 
4000 IU/day of vitamin D supplementation x 8 weeks; or 50000 IU (single dose) of vitamin D every other week x 4 doses total Vitamin D (<math>D_2+D_3</math>) level should be checked in 4 or 8 weeks and continue supplementation if still low
 
Once the Vitamin D level is normalized the participant would receive 600 IU/day of Vitamin D
 
	
 
calcium supplementation at a dose of 50 mg/kg divided 3x/day (max daily calcium dose of 2000 mg/day).
 
Check levels weekly, increase as needed if low.
 
Once ionized or corrected calcium is normalized, if dietary calcium is low, the participant would receive calcium 1,200 mg/day
 

ionized or corrected calcium level	normal		
dietary calcium intake based on questionnaire	low		

Age	$< 9$	Vitamin D	Calcium (elemental)
Vitamin D level ( $D_2+D_3$ ) T	20-29	
 
50000 IU (single dose) of vitamin D every other week x 2 doses total
 
Check Vitamin D (<math>D_2+D_3</math>) levels in 4 weeks
 
Continue vitamin D supplementation until Vitamin D levels normalize. Once normalized vitamin D would be given as part of multivitamin supplementation.
 
	
 
calcium supplementation at a dose of 50 mg/kg/day (max daily calcium dose of 2000 mg/day) or the maximum allowed per TPN
 
Check ionized or corrected calcium level every week
 

ionized or corrected calcium level	low		
Patient on TPN	Yes		

Age	$\geq 9$	Vitamin D	Calcium (elemental)
Vitamin D level ( $D_2+D_3$ ) T	20-29	
 
50000 IU (single dose) every other week x 4 doses total
 
	
 
calcium supplementation a dose of 50 mg/kg/day (max daily calcium dose of 2000 mg/day) or the maximum allowed per TPN
 

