### 7.3.3 Vitamin D Deficiency

Age	1-3 years	Vitamin D	Calcium (elemental)
Vitamin D level ( $D_2+D_3$ ) T	10-19	
 
4000 IU/day of vitamin D supplementation x 8 weeks. Vitamin D (<math>D_2+D_3</math>) level should be checked in 8 weeks
 
	
 
calcium supplementation at a dose of 50 mg/kg divided 3x/day (max daily calcium dose of 2000 mg/day) for 4 weeks
 

ionized or corrected calcium level	normal	
 
continue Vitamin D supplementation if still low
 
	
 
After 4 weeks of calcium supplementation, if dietary calcium is low, the participant will receive calcium 600 mg/day.
 

dietary calcium intake based on questionnaire	normal/low	
 
Once normalized the participant would receive 600 IU/day of Vitamin D
 
	
PTH*	$>65$		

\*When PTH is  $<65$  and Vitamin D level ( $D_2+D_3$ ) is 10-20 with normal ionized or corrected calcium and normal or low dietary calcium intake, calcium supplementation at a dose of 50mg/kg/day 3 times daily is not needed, otherwise follow the same supplementation guidelines.

Age	4-8 years	Vitamin D	Calcium (elemental)
Vitamin D level (D 2 +D 3 ) †	10-19	
 
4000 IU/day of vitamin D supplementation x 8 weeks. Vitamin D (D2+D3) level should be checked in 8 weeks
 
continue Vitamin D supplementation if still low
 
Once normalized the participant would receive 600 IU/day of Vitamin D
 
	
 
calcium supplementation at a dose of 50 mg/kg divided 3x/day (max daily calcium dose of 2000 mg/day) for 4 weeks
 
After 4 weeks of calcium supplementation, if dietary calcium is low, the participant will receive calcium 1,000 mg/day
 

ionized or corrected calcium level	normal		
dietary calcium intake based on questionnaire	normal/low		
PTH*	>65		

**\*When PTH is <65 and Vitamin D level (D2+D3) is 10-20 with normal ionized or corrected calcium and normal or low dietary calcium intake, calcium supplementation at a dose of 50mg/kg/day 3 times daily is not needed, otherwise follow the same supplementation guidelines.**

Age	≥9	Vitamin D	Calcium (elemental)

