Vitamin D level (D 2 +D 3 ) T	10-19	
 
50000 IU (single dose) of vitamin D every other week x 4 total doses.
 
Check Vitamin D (D2+D3) levels in 8 weeks
 
Continue vitamin D supplementation until Vitamin D levels normalize. Once normalized vitamin D would be given as part of multivitamin supplementation.
 
	
 
calcium supplementation a dose of 50 mg/kg/day (max daily calcium dose of 2.000 mg/day) or the maximum allowed per TPN
 
Check ionized or corrected calcium level every week
 

ionized or corrected calcium levels	normal or low		
PTH*	>65		
Oral intake	No		
Patient on TPN	Yes		

**\*When PTH is <65 and Vitamin D level (D2+D3) is 10-19 with normal ionized or corrected calcium, calcium supplementation at a dose of 50mg/kg/day 3 times daily is not needed, otherwise follow the same supplementation guidelines.**

Age	$\geq 9$	Vitamin D	Calcium (elemental)
Vitamin D level (D 2 +D 3 ) T	10-19	
 
50000 IU (single dose) every week x 8 total doses
 
Check Vitamin D (D2+D3) levels in 8 weeks
 
Continue vitamin D supplementation until Vitamin D levels normalize. Once normalized vitamin D would be given as part of multivitamin supplementation.
 
	
 
calcium supplementation a dose of 50 mg/kg/day (max daily calcium dose of 2.000 mg/day) or the maximum allowed per TPN
 
Check ionized or corrected calcium level every week
 

ionized or corrected calcium levels	normal or low		
PTH*	>65		
Oral intake	No		
Patient on TPN	Yes		

**\*When PTH is <65 and Vitamin D level (D2+D3) is 10-19 with normal ionized or corrected calcium, calcium supplementation at a dose of 50mg/kg/day 3 times daily is not needed, otherwise follow the same supplementation guidelines.**

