#### **7.4.3 Expected Toxicities**

The most common side effects in adults receiving pamidronate are hypertension, injection site reaction, hypocalcemia, hypokalemia, hypomagnesemia, hypophosphatemia, loss of appetite, nausea, vomiting, anemia, urinary tract infectious disease, cough, dyspnea, fatigue, and malaise. Other serious adverse effects that have been observed in adults are arthralgia, aseptic necrosis of bone of jaw, bone pain, myalgia, seizure, deteriorating renal function, focal segmental glomerulosclerosis, and nephrotoxicity.

In studies of pamidronate in children, hypocalcemia is also a common side effect. Brief acute phase reactions, including fever, headache, nausea, vomiting, rash, tachycardia, myalgia, and bone pain have also been noted on first exposure in pediatric patients. Uncommon side effects are nephrotoxicity, anterior uveitis, and atrial fibrillation. Due to these possible side effects, subjects will have laboratory evaluations performed to monitor for hypocalcemia or nephrotoxicity. Furthermore, any safety issue that might arise will be quickly recognized and treated as these subjects will be undergoing intensive monitoring following HCT.

Potential long-term side effects are radiographic metaphyseal bands, iatrogenic osteopetrosis, fractures after discontinuation of drug in growing children, delayed healing at osteotomy sites, esophageal cancer, and osteonecrosis of the jaw.

Long-term side effects are unlikely after a short-term treatment with pamidronate in patients without an underlying metabolic bone disease. There have been no reports of either esophageal cancer or osteonecrosis of the jaw in children after treatment with pamidronate.

Refer to the prescribing information for additional information.

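### Outside the weekly-calcium charts, no calcium is scheduled between discharge on the infusion day and the next dose about 90 days later, although serum is drawn for creatinine within 7 days

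*Combined protocol and SAP*

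**What the plan says.** **After each infusion.** Section 7.4.1 requires a same-day calcium: "A serum calcium level will be done after the pamidronate infusion end but prior to discharge from clinic". The further test for children on supplemental calcium is also same-day. For the days that follow, it says: "A serum creatinine and a spot urine albumin and creatinine will be scheduled for the morning after each pamidronate infusion", with up to 7 days allowed. Albumin here is a urine test, so creatinine is the only serum analyte. The one-week contact (8.1, 9.2) is by telephone.

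**Stated purpose.** Section 7.4.3 lists hypocalcemia as common in pediatric studies and states that "subjects will have laboratory evaluations performed to monitor for hypocalcemia or nephrotoxicity".

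**Scheduled calcium.** The ionized or corrected calcium row in 8.1 is marked at screening or study entry and Days 90, 180 and 270, not Day 360. Section 7.2 speaks generally of designated time points through Day 360. It also sends any child whose calcium is below range, whenever found, to section 7.3.

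**Weekly checks in 7.3.** Some charts order them:
- Low-calcium charts, for example "Check levels weekly, increase as needed if low" in 7.3.2.
- Parenteral-nutrition charts for vitamin D 10–19 ng/mL: "Check ionized or corrected calcium level every week".
- Oral-intake charts for vitamin D below 10: "Check ionized or corrected calcium every week and if low increase supplementation as needed to normalize ionized or corrected calcium".

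The three oral charts for vitamin D 10–19 with normal calcium order none. Their next step depends on diet rather than on a calcium result, as in the chart for ages 1–3: "After 4 weeks of calcium supplementation, if dietary calcium is low, the participant will receive calcium 600 mg/day".

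**Vitamin D as a bar.** Section 6.2 excludes children below 20 ng/mL from randomization because "use of pamidronate is contraindicated due to potentially higher risk of hypocalcemia". The hold list before each infusion in 7.4.1 names only raised creatinine and a positive pregnancy test. A low vitamin D leads to supplements there, not to a hold.

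**The concern.** The plan names a toxicity as common, commits to laboratory monitoring for it, and then, for children outside the weekly-check charts, schedules no calcium between leaving the clinic and the visit for the next dose. A fall that begins after discharge and causes no symptoms would be neither seen nor treated under 7.3. The plan already brings the child, or a sample, to a laboratory in the following week and does not use that serum for calcium.

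What is at stake is the safety of treated children, together with the completeness of the trial's information on a known effect of the drug. The primary efficacy comparison is not affected.

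**Working it through.** The plan states no interval between calcium tests, so there is no figure of its own to reproduce beyond the 3-month dosing interval.

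**1. Gap to the next scheduled calcium.** Windows come from 7.4.1 and 8.1: dose 1 Day 76–104, dose 2 Day 166–194, dose 3 Day 240–300, final visit Day 330–390. Shortest gap = earliest next visit minus latest infusion. Longest gap = latest next visit minus earliest infusion.

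| After | Nominal | Shortest | Longest |
|---|---|---|---|
| Dose 1 (to Day 180 visit) | 90 | 166 − 104 = 62 | 194 − 76 = 118 |
| Dose 2 (to Day 270 visit) | 90 | 240 − 194 = 46 | 300 − 166 = 134 |
| Dose 3 (only if 7.2 is read to require a Day 360 draw) | 90 | 330 − 300 = 30 | 390 − 240 = 150 |

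The nominal 90 days agrees with the 3-month interval. If a 14-day creatinine hold under 7.4.2 ran past the late edge of the window, the shortest gaps would be 166 − 118 = 48, 240 − 208 = 32 and 330 − 314 = 16 days. With calcium on the creatinine draw, the gap would be at most 7 days.

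**2. Who is outside the weekly checks.** Counting the charts in 7.3 as printed:

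| Calcium or vitamin D status on the chart | Charts | With weekly calcium check |
|---|---|---|
| Normal calcium (7.3.1: 4; 7.3.2: 5; 7.3.3: 3) | 12 | 1 |
| Low calcium (3 + 5 + 3) | 11 | 10 |
| Normal or low, parenteral nutrition, vitamin D 10–19 | 2 | 2 |
| Vitamin D below 10 (3 oral, 2 parenteral nutrition) | 5 | 3 (oral) |
| Total | 30 | 16 |

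Both exceptions are in 7.3.2, for age 9 or older with vitamin D 20–29: one chart labelled normal has the weekly check and one labelled low lacks it. They look like a single swap of labels. With that corrected, the rule is simple: among oral charts with vitamin D of 10 or more, weekly checks follow a low calcium and not a normal one. These are counts of charts, not of children.

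**3. Can a higher-risk child be infused without a later check?** Take a child with vitamin D of at least 20 at randomization who has 10–19 ng/mL before dose 2 or 3, with normal calcium and eating by mouth.
- The hold list in 7.4.1 does not stop the dose.
- Section 7.4.6 adds the exclusion criteria of 5.2, but the vitamin D bar is in 6.2. Only the investigator's general discretion remains.
- The 8.1 footnote on administration requires review of creatinine and pregnancy results only.
- The applicable chart rechecks vitamin D at 8 weeks and orders no weekly calcium.

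Unless the same-day test is low, the next scheduled calcium is the pre-dose draw after dose 2. After dose 3, 8.1 marks none.

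**4. Number of added assays.** Section 12.1 expects 86 children at Day 90. Even split: 86 / 2 = 43 treated, and 43 × 3 = 129. Section 12.3 allows a difference of 2 per age stratum at each site: 2 sites × 2 strata × 2 = 8, so up to (86 + 8) / 2 = 47 treated, and 47 × 3 = 141. Both figures assume that every treated child receives all three doses.

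**The case against.** The strongest case against is that the documents never say when calcium falls after pamidronate. Nothing in them shows that a test at the end of infusion misses the fall. The day ranges restate the dosing interval and do not measure missed events. This stands: no rate of missed hypocalcemia can be claimed.

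Next, the plan has real controls. Section 1.2 describes the hypocalcemia as transient and open to prevention or mitigation by supplements. Calcium and vitamin D are checked before each dose. A low value before infusion or on the same day sends the child to 7.3, usually with weekly rechecks. The one-week call and unscheduled visits can pick up symptoms. This also stands, and it narrows the gap to a fall that is both late and silent.

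The plan also relies on standard or intensive post-transplant monitoring (2.2, 7.4.3). This stands only in part. No calcium test or date is named, and 8.1.3 says that Day 270, the visit for dose 3, does not coincide with standard follow-up.

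Finally, a next-morning calcium may itself come too early, and the fix leaves the missing vitamin D hold untouched. Both are fair. The first is why the fix carries a caution. The second is a separate matter.

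A reader might infer that every child with vitamin D below 20 goes unchecked. The documents do not support this: those below 10 on oral intake, those at 10–19 with low calcium, and those at 10–19 on parenteral nutrition with PTH above 65 all have weekly checks. Nor does 11 of 12 normal-calcium charts mean that most children are unmonitored, because the documents do not say how many children fall on each chart.

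**Conclusion.** The point holds within limits. For treated children outside the weekly-check charts, scheduled calcium monitoring after an infusion ends with the same-day test. It resumes at the pre-dose draw about 90 days later (62–118 days after dose 1, 46–134 after dose 2). After dose 3 the schedule marks none. Against the purpose stated in 7.4.3, this is a gap that serum already being drawn could narrow.

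The size of the benefit is unknown, because the documents give neither the onset time nor the number of children affected. It would be wrong to read this as evidence that hypocalcemia is being missed, or that the plan does no monitoring for it: the pre-dose and same-day tests exist and lead to treatment. The ranges assume that doses and visits fall within their stated windows. Routine care may add calcium tests that the protocol does not list. This is a cheap improvement in safety monitoring, not a defect that undermines the trial.

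**What to change.** In 7.4.1, 8.1 and 8.3.2, add total calcium with albumin (or ionized calcium) to the serum creatinine draw made the next morning or within 7 days after each infusion. Record the day of the draw, treat low values under 7.3, and state that a normal next-morning value does not exclude a later fall.

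**Cost.** About 129 added calcium assays with an even split of 86, up to about 141 with the allowed imbalance, plus albumin where no value within 7 days is available (the allowance in 7.2). No new visit or needle is needed. A note to the table in 8.3.1 already puts total calcium and creatinine in one tube. It does not cover ionized calcium and is tied to no printed row, so total calcium with albumin is the simpler choice and the tube should be confirmed. Outside laboratories must be told to run calcium, and an amendment is required.

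**Downside.** The yield is uncertain, and an early normal result may give false reassurance.
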